1 INTRODUCTION

1.1 BACKGROUND

Atrial fibrillation (AF) is a major public health issue, with a high risk of frequent hospital admissions, stroke and premature death. AF affects at least 2 million people in the UK. Data from a large registry with over 4000 people with AF has shown that 11% will have an ischaemic stroke within 5 years, a five to seven-fold increase compared to stroke incidence in the general population. Furthermore, these strokes are likely to be more severe, or fatal. Consequently, almost 70% of people with an AF-related stroke will die, or be left with a permanent disability, compared to 55% of people with non-AF strokes.

An effective, evidence-based treatment to prevent AF related strokes exists. A systematic review including over 75,000 participants, showed effective treatment with oral anticoagulant medications (OACs), such as warfarin, or non-vitamin K OACs (NOACs), reduced the stroke risk in people with AF by two-thirds.³ The number needed to treat with warfarin to prevent a stroke is 25. Indeed, it is estimated that in England alone, appropriate management of AF can prevent around 7000 strokes and save 2100 lives per year.⁴

Despite this, 10% of all ischaemic strokes are in individuals with undiagnosed AF, which has led to a focus on AF detection in a range of settings, including general practice, community pharmacy, and out-patient clinics.⁵ A meta-analysis of patient-level data from 19 screening studies with 141,220 patients concluded that screening patients >65 years old, the detection rate of new AF cases is 1.44% (95% CI, 1.13%—1.82%), and 84% of new AF cases have a Class-1 recommendation for OAC prophylaxis.⁵ During the COVID-19 pandemic, opportunistic detection of AF has declined dramatically due to reduced interactions with healthcare providers such as general practitioners and pharmacists. One service that has continued to provide inperson care is the Newcastle Dental Hospital. However, no studies have investigated the potential to undertake a simple screening programme for AF in patients undergoing dental treatment.

Periodontal disease (PD) is strongly associated with cardiovascular disease. A recent study highlighted the high prevalence of AF in a population who have PD.⁶ In the dental Atherosclerosis Risk in Communities Study (ARIC) cohort, 5,958 were assessed without prior AF, 754 (13%) were found to have AF.⁶ Severe PD was associated with AF on both univariable (crude HR, 1.54; 95% CI, 1.26-1.87) and multivariable (adjusted HR, 1.31, 95% CI, 1.06-1.62) analyses. Mediation analysis suggested AF mediates the association between PD and stroke. In the main ARIC cohort, 9,666 participants without prior AF were assessed for dental care use, 1558 were found to have AF (16%).⁶

1.2 AF SCREENING IN DENTAL CLINICS

Dental clinics provide an ideal location, and an appropriate health professional/community interface, to screen people for AF. Approximately 90% of the UK population visits a dentist every two years making it one of the most accessible healthcare services in the community. Approximately 50% of the adult population have PD, with 30% of the population having treatment for active tooth decay.⁷ Those requiring specialist treatment of periodontal disease attend dental hospitals, thus those at highest risk of cardiovascular disease due to periodontal disease are likely to be found in these clinics. The NHS Newcastle Dental Hospital and School is the preeminent centre for specialist oral health care, education and research in North England. The Dental Hospital is one of the largest integrated teaching and hospital complexes in the UK, which includes 3 community outreach clinics. The Dental Hospital and School provides a range of dental services and a recent audit showed that in one month over 2500 patients over the age of 65 years attended for treatment. We aim to test if dental clinics are a suitable place to identify previously undetected AF during and beyond the COVID-19 pandemic. The study will aim to 1) determine if there is any correlation between severity of dental disease and AF incidence; 2) test a pathway to ensure that patients are appropriately managed following detection of AF; and 3) to determine cost-effectiveness of identification of AF in dental settings.

1.3 RATIONALE FOR STUDY

Date: 30/5/2022 Version: 6

AF is prevalent, affecting approximately 5% of those aged 65 years and older. Unrecognised AF is generally not associated with symptoms and raised resting heart rate. Those with unrecognised AF usually have stroke risk scores (i.e., CHA2DS2 VASc scores) high enough to warrant anticoagulation. Furthermore, registry data suggests that incidence of AF may be much higher in a population who have periodontal disease, which generates the hypothesis that there are appreciable numbers who would benefit from early recognition of AF through simple detection programmes, followed by thromboprophylaxis to prevent future stroke.

This study aims to determine the appropriateness and impact of dentistry-based screening, using innovative technology (a single/six lead ECG device, KardiaMobile) that has been used in numerous AF screening studies, focused on identifying people with undiagnosed AF, with onward referral to their GP for appropriate medical management of AF. The study also aims to explore the role of dentists in ongoing management of AF, as well their role in raising AF awareness in the public.

The findings of this study will have broad implications for the general population aged 65 years and older with undiagnosed AF. We anticipate that the study will demonstrate that it is possible to identify and treat people in the community, not identified due to COVID-19 restrictions, who were not previously known to have AF, thus greatly reducing the risk of stroke. Findings from this study will inform the design and refinement of a future intervention for large-scale research and implementation.

2 STUDY AIM and OBJECTIVES

2.1 **Aim**

The study aims to test if dental clinics are a suitable place to identify previously undetected AF during and beyond the COVID-19 pandemic. It will determine if there is any correlation between severity of dental disease and AF incidence; test a pathway to ensure that patients are appropriately managed following detection of AF; and determine cost-effectiveness of identification of AF in dental settings.

Primary Objective:

Edinburgh Napier

• To identify the proportion of screened participants with newly identified AF in attending a dental clinic aged 65 years and older.

Secondary Objectives:

- To examine the correlation between periodontal health/disease status; age, sex; ethnicity; Index of Multiple Deprivation; and incidence of AF.
- To assess the suitability and cost-effectiveness of AF screening in a dental setting.

2.2 Primary Endpoint/Outcome Measure

The primary outcome measure will be the proportion of screened subjects with newly identified AF attending a dental clinic aged 65 years and older.

STUDY DESIGN

(Phase 1) A cross-sectional study of screening in dental clinics to identify undiagnosed AF in adults aged 65 years and over. (Phase 2) A qualitative study of healthcare professionals involved in the care of phase 1 study participants to explore factors that might influence sustainability of screening processes beyond the study setting.

STUDY POPULATION

2.3 NUMBER OF PARTICIPANTS

All patients attending the Dental Hospital will be eligible to participate if they are aged 65 years or older (n=1000). Additionally, a sub-sample of dental hospital staff/students and general practitioners involved in the care of the participants will be asked to take part in a qualitative telephone interview (n-20).

2.4 INCLUSION CRITERIA

The following people will be eligible to take part in the study:

Phase 1: patient screening:

Adults aged 65 years and over

- Being a patient of the Newcastle dental hospital
- · Able to give informed consent
- Due to time and financial constraints surrounding the cost translation services and qualitative data transcription, the study will be unable to recruit participants who cannot adequately understand verbal explanations or written information given in English.

Phase 2: healthcare professionals' interview:

- Dental hospital staff/students working at the Newcastle Dental Hospital involved in the care of study participants
- GPs involved in the care of study participants.

2.5 EXCLUSION CRITERIA

The following people will not be eligible to take part in the study:

Phase 1: patient screening:

- Have been diagnosed with severe co-existing conditions (severe dementia or terminal illness)
- Are unable to give informed consent
- Due to time and financial constraints surrounding the cost translation services and qualitative data transcription, the study will be unable to recruit participants who cannot adequately understand verbal explanations or written information given in English

Phase 2: healthcare professionals' interview:

- Dental hospital staff/students who are not working at the Newcastle Dental Hospital and not involved in the care of study participants
- GPs who are not involved in the care of study participants

3 PARTICIPANT SELECTION AND ENROLMENT

3.1 RECRUITMENT OF PARTICIPANTS

Phase 1: patient screening

Patient participants (n=1000) will be recruited via two mechanisms: 1) Posters advertising the screening study will be located at the entrance to and within the Dental Hospital inviting patients to directly contact research staff who will be available around the building to help recruitment [Appendix 1]. 2) Dental hospital staff and dental students will ask patients attending for appointments whether they are interested in participating and provide written information about the study (participant invitation [Appendix 2], participant information sheet [Appendix 3], privacy notice [Appendix 4] and consent form [Appendix 5]). The participant information sheet will include an explanation of the screening process, and that information will be shared with their GP if abnormal rhythms are detected. This will include the electrocardiograms (ECGs) collected during the screening process. Participants will also be informed that they may be required to have follow up with the GP if abnormal findings are detected.

The intervention flow chart is displayed in Figure 1.

[figure not shown]

Figure 1 Patient Screening flow chart

Date: 30/5/2022 Version: 6

Phase 2: healthcare professionals' interviews:

Prior to the start of the study, dental staff and students at the Newcastle Dental Hospital and GPs in the area surrounding the Newcastle Dental Hospital will be sent study information via email (using agreed NHS gatekeepers). This will include an invitation to take part in the healthcare professional element of the study [Appendix 6], a study information sheet [Appendix 7], a privacy notice [Appendix 8] and a link to an online consent form [Appendix 9]. Interested healthcare professionals will complete an online consent form via Novi Survey to register for the study.

Optional education about AF will be offered to any participating interested health care professionals. The training will include information about the causes of AF, symptoms and evidence- based management, the health risks associated with AF, self-care management and cardiovascular risk reduction. Interested team members will also be trained to operate the KardiaMobile device (handheld single-lead/six-lead ECG) and interpret the single-lead ECG trace recording. Training of the team will be undertaken structured training module, using using а combination of online (https://www.escardio.org/Education/E-Learning/Webinars/detection-and-diagnosisof-atrial-fibrillation), centralised and onsite training, designed and delivered by a senior cardiologist, specialist nurse, and periodontal surgeon. Participating members of the training module will be eligible to claim Continuing Professional Development points on completion.

Towards the end of patient data collection, NHS gatekeepers will again circulate information via email about the qualitative interview element of the study to healthcare professionals who have been involved in the care of patients who are participating in the study. This will be the same information sent at the beginning of the study.

CONSENTING PARTICIPANTS

Phase 1: patient screening:

Recruitment will take place at the Newcastle Dental Hospital. Patients eligible and interested in participating in the study will be given study information [Appendix 2, 3]

Date: 30/5/2022 Version: 6

and 4] and a consent form [Appendix 5] by the staff at Newcastle Dental Hospital when they attend for their routine appointment. If patients wish to participate, they will talk to an appropriately trained member of the research team and decide whether they want to take part. An appropriately trained member of the research team will gain written informed consent from all participants prior to conducting the screening assessment. The consent forms will be signed by the participant and a suitable member of the research team who is on the delegation log for this task and GCP trained. Two copies will be taken, one for the participant, one for the dental records. The original will be put in the Investigator Site File which will be stored securely in the Dental Clinic Research Facility. Participation will be voluntary and choosing not to take part will not affect their usual dental care.

The participant will be given every opportunity to clarify any points they do not understand and, if necessary, ask for more information from the dental staff and the study nurse. If participants want to talk to an independent person about the study, details will be included in the Participant Information Sheet [Appendix 3] to facilitate this. The participant will have sufficient time to consider the information provided.

Phase 2: healthcare professionals' interview:

Prior to the start of the study, dental hospital staff and students at the Newcastle Dental Hospital, and GPs in the area surrounding the Newcastle Dental Hospital will be sent study information via email (using agreed NHS gatekeepers). This will include a study invitation to take part in the healthcare professional element of the study [Appendix 6], information sheet [Appendix 7], a privacy notice [Appendix 8] and an online consent form [Appendix 9]. Interested healthcare professionals will return the consent form to the principal investigator to register for the study. Towards the end of patient data collection, NHS gatekeepers will again circulate information via email about the qualitative interview element of the study to healthcare professionals who have been involved in the care of patients who are participating in the study. This will be the same information sent at the beginning of the study.

If participants want to talk to an independent person about the study, details will be included in the Participant Information Sheet to facilitate this. The participant will have sufficient time to consider the information provided.

Edinburgh Napier

3.2.1 Withdrawal of Study Participants

Study information will emphasise that the participant may withdraw their consent to participate at any time by contacting a member of the research team. Study data can be withdrawn up until the point that data analysis is completed. This will be made clear in the supporting documentation pre-study. At the end of the study, participants will be provided with a participant debrief summary [Appendix 10], which will reiterate this.

4 STUDY PROCEDURE

4.1 STUDY ASSESSMENTS

Phase 1: patient screening:

The study nurse will complete the following screening protocol:

- The screening will be approximately 5min duration.
- Screening will consist of an initial brief medical history, including pharmacotherapy and screen of AF symptoms. We will also ask for date of birth, sex, ethnicity, postcode so that we can link Basic Periodontal Examination to participants. We will also ask for telephone number and registered GP/GP surgery address only in the case of abnormal rhythm or inconclusive rhythm so that we are able to inform the GP of results and follow up participants [Appendix 11].
- The study team will assess cardiac rhythm using the single-lead recording function on the handheld KardiaMobilie ECG device for 30s. The KardiaMobile ECG device will be the property of ENU and will be in the possession of the study nurse during assessments. The device will not be on participants personal mobile telephones.
- The ECG record with a unique identification number will be transmitted by wireless connection on a secure server to an iCloud by the KardiaMobile software. The ECG record is only accessible by the study team.
- The study team will advise the participant of the suspected diagnosis and ensure they understand the next steps in the pathway
- For every person with an abnormal ECG (not AF), the study team will offer a 6-lead ECG using the KardiaMobile 6-lead functionality. KardiaMobile

Date: 30/5/2022 Version: 6

records Leads I,II,II, AVL, AVR, and AVF by additional electrode placement on left knee or ankle.

At the end of the screening, participants will be given a participant debrief sheet [Appendix 10] and those with a normal rhythm will be given a letter stating that no further action is required [Appendix 16].

Protocol if AF is not suspected from the screening

GP will not be informed of the participant screening.

Protocol if a diagnosis of AF is suspected from the screening

• The study nurse will counsel the participant and advise that their GP will be contacted to arrange follow up.

- Edinburgh Napier University researchers will send a typed letter to the GP explaining the potential diagnosis, which will include a copy of the ECG recording. If required, the letter will include an invitation to refer their patient for a full assessment at any cardiology service of their choosing. A copy will be inserted in the patient notes at Newcastle Dental Hospital.
- The study team will call the participant approximately 1 month after the date of screening, to ensure they have not been lost to follow-up.
- The study team will call the GP surgery to determine if any treatment or further follow up was required.

Protocol if a diagnosis of AF is not suspected from the screening but an abnormal rhythm is detected

- Those participants with an abnormal rhythm detected on single lead ECG, not previously identified, will be offered a 6-lead ECG on the KardiaMobile. This involves placing an additional electrode on either the left knee or left ankle and takes 30 seconds as for a single-lead recording.
- They will be counselled by the study nurse regarding the diagnosis and advised to return to their GP to discuss the next phase of their management.

- Edinburgh Napier University researchers will send a letter to the GP explaining
 the potential diagnosis, which will include a copy of the 6-lead ECG recording,
 and an invitation to refer their patient for a full assessment at any cardiology
 service of their choosing. A copy will be inserted in the patient notes at
 Newcastle Dental Hospital.
- If the GP refers the participant to the cardiology clinic, the full assessment will be performed by a Cardiologist, according to standard cardiology practice, and will include a 12-lead ECG. If appropriate, the patient may be commenced on appropriate thromboprophylaxis, according to evidence-based guidelines ⁷
- The study team will call the participant approximately 1 month after the date of screening, to ensure they have not been lost to follow-up [Appendix 12].

Protocol if a history of AF is known prior to the screening

 Edinburgh Napier University researchers will send a letter to the participant's GP informing them that their patient was screened for AF, stating if they were in sinus rhythm or AF on the day of the screening.

Linking to periodontal health/disease

 The consent form will include consent for dental hospital staff to provide the Basic Periodontal Examination (BPE) result for each routinely conducted at their appointment (Table 1).

Table 1 E	Table 1 Basic Periodontal Examination		
0	This indicates that there are no pockets >3.5mm (i.e. the black band is completely visible), no bleeding and no calculus or plaque traps (e.g. overhanging restorations)		
1	This indicates that there are no pockets >3.5mm (i.e. the black band is completely visible), no calculus or plaque traps (e.g. overhanging restorations) but there is bleeding after probing		
2	This indicates that there are no pockets >3.5mm (i.e. the black band is completely visible) but there is calculus or plaque traps present		

Edinburgh Napier

3	This indicates that probing depths between 3.5mm and 5.5mm have
	been found (i.e. black band is partially visible)
4	This indicates a probing depth of >5.5mm (i.e. black band is completely hidden in pocket)
*	Indicates furcation involvement

The study team will provide a list of all participants in an encrypted excel spreadsheet (name, date of birth and address) to allow for identification to the dental hospital staff. The dental hospital will provide the result of the basic periodontal examination for each participant on an encrypted excel spreadsheet. Patients will give written consent for this data to be shared with the study team, and an appropriate data-sharing agreement will be in place between Edinburgh Napier University and Newcastle Dental Hospital.

Phase 2: healthcare professionals' interview:

Upon completion of phase one, healthcare participants will be asked to take part in an individual qualitative telephone interview with an Edinburgh Napier University researcher. A semi-structured interview schedule [Appendix 13] will be referred to in the telephone interview. We will explore the barriers and enablers to the screening processes in the AF detection programme and the effects it has had on the reported practice of the healthcare professionals involved with the participant. At the end of the interview, participants will be emailed a participant debrief sheet [Appendix 10].

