5.1.2 Data analysis

Phase 1: patient screening:

Primary analyses will be conducted using SPSS (V26). New episodes of AF will be expressed as true positives divided by total number screened with accompanying 95% CIs. A sample size of 1000 will provide a CI of 60.8% assuming an incidence of 1.6%. χ^2 tests will be used to compare new cases by sex and to identify associations between AF incidence and age group or AF risk factors. A Pearson's or Spearman's correlation test, depending on normality of data, will be used to assess the strength and the direction of relationships between parameters. A two-sided p value of < 0.05 will be considered significant.

Cost-effectiveness

A previously tested decision-analytic Markov model⁸ will be used to simulate the risk of stroke and bleeding events with standard case finding of newly identified AF (i.e. no screening/usual care) and to then assess the impact that screening with single lead ECG would have on the downstream costs and health outcomes over a 30 year time

Edinburgh Napier

horizon. Costs incorporated in the model will include those associated with screening, drugs to offset the risk of stroke (i.e., warfarin or NOACs), adverse events (e.g., systemic embolism, stroke) and the potential complications of warfarin and NOAC treatment (e.g., intracranial haemorrhage, clinically relevant bleed). Health-state utilities associated with pre and post treatment will be incorporated in the model to calculate QALYs. A ceiling ratio of £30,000 per QALY to delineate the cost-effectiveness of opportunistic screening will be applied. Costs and benefits (QALYs) will be discounted at the NICE recommended rate of 3.5% per annum in line with the NICE reference case. Model inputs will be based on several available evidence sources including previous work in AF screening in Scotland. Extensive deterministic sensitivity analysis along with probabilistic sensitivity analysis will be undertaken to investigate model assumption and parameter uncertainty on robustness of the results.

Phase 2: healthcare professionals' interview:

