1.2 Types of data

The study involves two phases.

Phase one will include primary quantitative data collected verbally from the subject comprised of medical history including pharmacotherapy and AF symptoms, date of birth, sex, ethnicity, address, postcode, telephone number and registered GP/GP surgery address and ECG cardiac rhythm using KardiaMobile ECG device. Additionally, a basic periodontal examination result will be collected from the patients NHS dental records via agreed NHS gatekeepers.

Phase two will include primary qualitative data collected via audio-recorded telephone semi-structured interviews of healthcare professionals involved in the care of study participants recruited in phase one. Topics will include experiences of the study, barriers and facilitators to AF screening in dental hospitals and views about follow up pathways.

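### Whether AF is newly identified rests on self-reported history, and the planned GP-surgery call is not stated to check for an earlier diagnosis, so an unreported known case can enter the primary numerator

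*Combined protocol and SAP*

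**What the plan says.** Section 2.2 defines the outcome: "The primary outcome measure will be the proportion of screened subjects with newly identified AF attending a dental clinic aged 65 years and older". The protocol does not say what makes a case new. Section 5.1.2 gives the estimator: "New episodes of AF will be expressed as true positives divided by total number screened with accompanying 95% CIs". It does not define a true positive.

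Known AF is not among the exclusion criteria in section 2.5, and section 4.1 has a separate pathway for participants with a known history. Each participant in AF on the trace must therefore be sorted into new or known.

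The visible basis for sorting is the screening visit of about five minutes: "Screening will consist of an initial brief medical history, including pharmacotherapy and screen of AF symptoms". The data management plan (Appendix 15, section 1.2) confirms the source: "Phase one will include primary quantitative data collected verbally from the subject comprised of medical history including pharmacotherapy and AF symptoms". Appendix 11 records the answers as a history tick-box for AF, a medication list (including anticoagulants, antiarrhythmics and digoxin) and a result category for AF already known. The only item the plan draws from health records is the periodontal examination result.

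After screening, two contacts are planned where AF is suspected. The one-month participant call (section 5.1.1 and Appendix 12) covers what has happened since screening: referral, 12-lead ECG, drugs, cardioversion or ablation. The other contact is with the surgery: "The study team will call the GP surgery to determine if any treatment or further follow up was required".

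**The concern.** The word that defines the primary outcome has no visible check against a record. A participant may have forgotten, misunderstood or simply not mentioned an earlier diagnosis. If that person is in AF during the 30-second trace, the visit yields an apparent new case. Nothing in the visible text would later move that case to the known group: the surgery is not stated to be asked, Appendix 12 does not ask, and no rule uses the medication list to query an answer of no AF history.

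With about 16 cases expected in 1000, a few such cases would shift the headline yield noticeably in relative terms. The bias comes from classification, so a larger sample would not remove it and the interval would not show it.

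**Working it through.** **The plan's own precision.** Section 5.1.2 reads: "A sample size of 1000 will provide a CI of 60.8% assuming an incidence of 1.6" percent. With n = 1000 and p = 0.016, the Wald half-width is 1.96 × √(0.016 × 0.984 / 1000) = 0.0078, or ±0.78 points (interval 0.82% to 2.38%). This agrees with ±0.8. The printed 60.8 is probably a corrupted ± sign, and nothing here depends on it.

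**Weight of one case.** Expected cases: 1000 × 0.016 = 16. One misclassified case adds 1/1000 = 0.1 point, or 1/16 = 6.25% relative.

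**Expected number of false new cases.** k = n × (share with known AF) × f × s, where f is the share of known cases not reported and s is the share of known cases in AF on the trace.

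- Share with known AF: the nearest figure is in section 1.3, "AF is prevalent, affecting approximately 5% of those aged 65 years and older". It is overall prevalence and is not split into diagnosed and undiagnosed, so 5% is only an anchor. Assumed range: 3% to 8%.
- f and s are not in the documents. Assumed ranges: f from 2% to 20%, s from 50% to 100%.

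| Known AF | f | s | k | Proportion if 16 cases are truly new |
|---|---|---|---|---|
| 5% | 2% | 0.5 | 0.5 | 1.65% |
| 5% | 5% | 0.5 | 1.25 | 1.73% |
| 5% | 10% | 0.5 | 2.5 | 1.85% |
| 5% | 10% | 1.0 | 5 | 2.10% |
| 5% | 20% | 1.0 | 10 | 2.60% |
| 3% (low extreme) | 2% | 0.5 | 0.3 | 1.63% |
| 8% (high extreme) | 20% | 1.0 | 16 | 3.20% |

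In the other direction, suppose 16 apparent new cases are observed and f is 5-10% with s = 0.5. The truly new proportion is then (16 − 1.25)/1000 = 1.475% down to (16 − 2.5)/1000 = 1.35%.

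**Against the planned precision.** The bias equals the half-width at 0.00778 × 1000 = 7.8 cases. With 5% known AF, that needs f = 7.8/(50 × 0.5) = 31% if half are in AF on the trace, or 7.8/50 = 16% if all are.

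**What the check could change.** If 16 cases are observed and the surgery shows that 3 were already on record, the estimate moves from 1.6% (Wilson 95% CI 0.99% to 2.58%) to 1.3% (0.76% to 2.21%).

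**The case against.** The strongest reply is that the concern argues from silence. The estimator counts true positives, which implies some confirmation. The GP receives a letter with the ECG and then a call, and for a patient already diagnosed the natural answer is that AF is known and managed. The nurse also has the medication list in view, and no visible form or script covers the surgery call. The screening flow chart and the consent pages are not visible, so a check described only there cannot be excluded.

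Part of this stands. The right wording is that such cases can be counted as new, not that they will be. But a true positive most naturally means that AF is present, not that it is new. A GP's unprompted remark has no field to go into, and no rule says what to do with it.

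A reader might also infer more than the documents support:

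- *That misclassification runs only one way.* It does not. A participant who wrongly reports earlier AF and is in AF on the day goes to the known-AF pathway and is lost from the numerator. The upward bias described here comes from unreported diagnoses, and the fix addresses only those.
- *That cost-effectiveness is inflated.* Section 5.1.2 says the model draws its inputs from several evidence sources, including earlier Scottish work. It does not say that this study's yield drives the model.
- *That the 5% in section 1.3 is diagnosed AF.* The text does not say so.
- *That an anticoagulant on Appendix 11 reveals a known case.* The same form lists thromboembolism and vascular disease, so the drug may have another indication.

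**Conclusion.** The concern holds in a limited form. In the visible text, the split between new and known AF depends on what the participant reports at the visit, and the one planned contact that could verify it is not stated to do so. An unreported earlier diagnosis can therefore raise the primary proportion.

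The size is unknown because the documents give no non-reporting rate. About 1 to 3 cases (0.1 to 0.25 points, 8% to 16% relative to 16) is a working figure that rests on 5% known AF, 5-10% non-reporting and half in AF on the trace. On those assumptions the bias is well inside the planned ±0.8 points and does not threaten the study. It is still worth correcting, because the confidence interval does not carry it and the correction is cheap.

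**What to change.** 1. Add one item to the GP-surgery call already planned for suspected AF: *Was AF recorded before the screening date? (Y/N, date)*. Provide a field to record the answer.
2. Define a case as newly identified only if there is no self-reported history and no earlier GP record. Move cases found on record to known AF.
3. Where the surgery gives no answer, keep the case in the primary count. Report a sensitivity analysis that leaves out unverified cases listing an anticoagulant or antiarrhythmic drug on Appendix 11, and state that these drugs have other indications.
4. Report how many cases were verified, reclassified and unverified.

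The cost is one question in calls already planned: about 16 if the expected yield holds, and more if some suspected traces prove not to be AF. Sample size, precision formula and participant contacts do not change. The yield may fall slightly, and the consent wording must be checked to make sure it covers asking the surgery about earlier diagnoses.
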